There are many reasons why patients are non-adherent to the HF plan of care. They may know what to do, but not how to incorporate change into their daily routine.⁸ Patients may have impaired memory, cognitive decline, lack of social support,⁹⁻¹¹ have general or exertional fatigue,¹² be older, have polypharmacy, poor sleep and comorbid conditions,¹³ and have cultural, socioeconomic, psychological, or physiological reasons.¹⁴ In a study that assess factors associated with 7-day follow-up appointment adherence, researchers used medical record and Centers for Medicare and Medicaid billing data and found that greater distance from the doctor's office, black race, rural address, lower socioeconomic status and women were associated with non-adherence.¹⁵ Further, patients' (and caregiver) acceptance of HF as a chronic condition that requires self-care actions, even when asymptomatic, may not be well understood; however, in one study, patients acceptance of HF was the only independent predictor of quality of life in the energy, pain, emotional reactions, sleep, social isolation and mobility domains.¹⁶

In addition to the many factors that may predict non-adherence to HF self-care, at hospital discharge, patients may be overwhelmed with materials and messages and may be unable to discern what self-care behaviors to focus on. Lay caregivers may not be present or may have misperceptions about self-care expectations. Repetition of messages is an age-old way to

enhance understanding of communication.¹⁷ However, it is unknown if a card with a standardized recordable messages specific to HF self-care, that can be replayed repeatedly after discharge, will enhance knowledge of expected self-care behaviors that leads to improved adherence, and improved clinical outcomes after discharge.

Study Purposes

The purposes of this study are to test the effects of a novel card with recorded discharge instructions that can be replayed on-demand post-discharge in the home, called “My Recordable On-Demand Audio Discharge (MyROAD) Instructions” card.

The following outcomes will be assessed:

1. 45-, 90-, and 180-day *first occurrence* of post-discharge all-cause and HF hospitalization, emergency department [ED] visit, and death or cardiac transplantation/ ventricular assist device [VAD] implant),
2. 45-, 90-, and 180-day *time to* first occurrence of all-cause and HF hospitalization, ED visit, or death/cardiac transplantation or VAD implant,

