3. 45-day quality of life, functional status and perceived adherence to activity/exercise recommendations,
4. 7-day follow-up appointment with the healthcare provider assigned before discharge.

Specific aims and hypotheses:

1. Determine the effects of MyROAD on *first occurrence* and *time to first occurrence* of all-cause and HF hospitalization, ED visit, and death (or cardiac transplantation or VAD).

Hypothesis 1a: 45-day post-discharge rehospitalization, ED visit and death will be lower or trend toward lower, and 90- and 180-day first occurrence of hospitalization, ED visit and death will be lower in the MyROAD group compared to the usual care group.

Hypothesis 1b: Time to first event (rehospitalization, ED visit and death) will be longer in the MyROAD group compared to the usual care group at 90- and 180 days.

2. Determine the effects of receiving repetitive HF messages via MyROAD on quality of life, functional status and perceived adherence to activity recommendations.

Hypothesis 2a: Health-related quality of life (specifically, the clinical summary score, quality of life score, total symptom score -and subscales of physical limitations, symptom stability, symptom frequency, and symptom burden- will be higher in the intervention group compared to the usual care group at 45-days, reflecting improved early post-discharge quality of life. [Note: overall summary score (that includes the areas above and also self-efficacy) will be measured but are not included in the endpoint.]

Hypothesis 2b: HF-related symptoms will be less prevalent in number in the MyROAD group compared to the usual care group at 45-days.

Hypothesis 2c: Functional status will be higher in the intervention group compared with the usual care group at 45-days.

Hypothesis 2d: Perceived highest activity/exercise level will be higher in the intervention group compared with the usual care group at 45-days.

3. Determine the effects of receiving repetitive HF messages by MyROAD on adherence to 7-day follow-up appointment after index discharge.

Hypothesis 3: Adherence to 7-day follow up appointment will be higher in the intervention group compared with the usual care group.

METHODS

Design: The study will use a 2-group, randomized, placebo-controlled, single blinded, design. Healthcare providers will be initially blinded to group assignment, but may learn about the card from patient verbalization over time, as it is not possible to blind patients to the intervention, a MyRoad card.

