9. Wheelchair bound, uses a cane or walker, or unable to carry out physical activity, including walking, due to a chronic disability or documented medical condition.

Intervention

MyROAD is a card that has been designed by CC innovators and American Greetings. When the card is opened, there is a general message that is automatically played. Within the card is a heart shaped cutout that has 4 buttons, one in each quadrant. When pressed, each button has audio of one aspect of general HF education: diet, medications, signs and symptoms of worsening condition and physical activity. The buttons can be pressed as desired (for approximately 2 weeks, until the battery expires) to allow playback of messages. At the top of the heart is a space for the phone number of who to call with questions. CCF Marketing and Brand team has been involved in card art and wording including, color choices, formatting, designs and branding/logos. A magnet allows the heart to adhere to metal surfaces as a visual reminder of self-care; see [Appendix A](#). The script was developed by a HF expert clinician ([name]) and reviewed and approved by [name], vice chair of Cardiology and section head of Heart Failure and Cardiac Transplantation in the Heart and Vascular Institute; see [Appendix B](#). The speaker of the script is a professional radio voice (hired by American Greetings). The card material can be written on, as desired by a health care provider; for example, a nurse can write down the specific dietary sodium limit/day or a phone number. The HF discharge instructions are short, global versions of discharge instructions used by Cleveland Clinic and match current global discharge instruction messages on self-care found in our HF Handbook and HF zones sheet, used by all CC hospitals in Northeast OH.

Outcomes and Measurement

Case report forms will be used to collect all-cause and HF hospitalization, ED visit, and death (or cardiac transplantation or VAD) healthcare consumption and also, 7-day adherence to the scheduled post-discharge follow-up appointment.

- Data will be collected at baseline and 45-, 90-, and 180-day days after discharge

Quality of life will be measured using the *Kansas City Cardiomyopathy Questionnaire* (KCCQ). Kansas City Cardiomyopathy Questionnaire (KCCQ) is a 23 item questionnaire that measures

V1_01-20-16

NCT02901314

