Based on historical readmission rates among subjects receiving the current standard of care treatment (~ 20% and dropping slightly every year), a 30-day readmission rate of 18% is expected. We are also basing the sample size on an expected 90-day rehospitalization rate of 25% and a 180-day rehospitalization rate of 35%; both of which are conservative. Sample size calculations were performed to show minimum sample size needed to detect a decrease of 30% at 30-days, 90-days and 180-days with the addition of the card. In many research studies, trends toward improvement are found at 30 days, but the trend is not significant till further out (90 days or 180 days). Thus, we are hypothesizing that a trend will be seen at 30 days, but that there will be significant differences at 90 days and 6-months. A total sample size of 968, 734 and 468 are needed to achieve 80% power in 30-day, 90-day and 180-day rehospitalization rates, respectively. These calculations assumed a balanced randomization and use of one-sided Pearson chi-square tests with a significance level of 0.05. Calculations were performed using SAS software (version 9.2; Cary, NC). To account for attrition in follow-up, sample size was increased by 10-% at 30-days and 20% at 90- and 180-days, creating ideal sample sizes of 1066 (533 per group; to achieve power at 30-days), 882 (441 per group; to achieve power at 90-days) and 562 (281 per group; to achieve power at 180-days).

- Thus, our *minimum sample size* will be 562 subjects. If trends in outcomes are favorable, data collection will continue to reach the required sample size for 90-day outcomes.

Analyses

Patient characteristics will be summarized using frequencies and percentages for categorical factors, and means, standard deviations, and percentiles of interest for continuous measures. Pearson chi-square tests will be used to compare the proportion of subjects meeting the composite endpoint of death or at least 1 readmission by 6 months. Secondary analyses will use Poisson regression to compare readmission rates (number of readmissions/follow-up days), and competing risk survival methods will be used to compare time to first readmission between groups. Analyses will be performed assuming a 0.05 significance level. Analyses will be performed using SAS software (version 9.2 or higher; Cary, NC).

Feasibility

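### Hypothesis 1b (time to first rehospitalization, ED visit or death) has no planned test, and ED visits are collected but never analysed

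*Combined protocol and SAP*

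**What the plan says.** All references are to the combined protocol and SAP.

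- **Study Purposes**, second outcome: time, at 45, 90 and 180 days, to "first occurrence of all-cause and HF hospitalization, ED visit, or death/cardiac transplantation or VAD implant".
- **Specific aims and hypotheses**, Aim 1: both first occurrence and time to first occurrence of "all-cause and HF hospitalization, ED visit, and death (or cardiac transplantation or VAD").
- **Hypothesis 1a**, in part: "90- and 180-day first occurrence of hospitalization, ED visit and death will be lower in the MyROAD group".
- **Hypothesis 1b**, for 90 and 180 days: "Time to first event (rehospitalization, ED visit and death) will be longer in the MyROAD group".
- **Outcomes and Measurement**: case report forms will "collect all-cause and HF hospitalization, ED visit, and death (or cardiac transplantation or VAD) healthcare consumption".
- **Analyses**: three between-group outcome comparisons are planned. The first is a Pearson chi-square test on the "composite endpoint of death or at least 1 readmission by 6 months". The other two are labelled secondary. One is a Poisson model for the number of readmissions per day of follow-up. For the other, "competing risk survival methods will be used to compare time to first readmission between groups".
- **Sample Size**: the totals of 968, 734 and 468 are for rehospitalization rates at 30, 90 and 180 days.

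**The concern.** A hypothesis about time to a first event needs an analysis in which each component of that event counts. Here the stated time-to-event analysis uses a narrower event than the stated hypothesis. This is more than missing detail: the plan names an analysis, and it answers another question.

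Two things are at stake. First, ED visits are part of Aim 1 and of Hypotheses 1a and 1b, but the plan gives no way to report an effect on them. Second, a favourable result for time to readmission might be read as support for Hypothesis 1b. Depending on the competing-risk method, that result may be unaffected by extra deaths in one arm, or may even look better because of them.

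**Working it through.** **Step 1. Event definitions side by side.**

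| Place | Rehospitalization | Death | ED visit | Transplant/VAD |
|---|---|---|---|---|
| Study Purposes; Aim 1 | yes | yes | yes | yes |
| Hypotheses 1a, 1b | yes | yes | yes | not named |
| Sample Size | yes | no | no | no |
| Chi-square, 6 months | yes | yes | no | not named |
| Poisson rate | yes | no | no | not named |
| Competing-risk time to event | yes | not as an event | no | not named |

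No analysis row has an entry for ED visits. The only time-to-event row has readmission alone as its event. The row for Hypothesis 1b matches no analysis row.

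**Step 2. What the sample size covers.** Inputs from Sample Size: control rehospitalization of 35% at 180 days and 25% at 90 days, a 30% decrease (read as relative), one-sided 0.05, 80% power, equal arms. Per arm,

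n = [z(0.95)·√(2p̄(1−p̄)) + z(0.80)·√(p₁(1−p₁)+p₂(1−p₂))]² / (p₁−p₂)²

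- 180 days, 0.35 v 0.245, p̄ = 0.2975: (1.645×0.6465 + 0.8416×0.6422)² / 0.105² = 2.573/0.011025 = 233.4, so 234 per arm and 468 in total. This matches the plan.
- 90 days, 0.25 v 0.175: 367 per arm and 734 in total. This also matches.

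Both totals follow from rehospitalization rates alone. No rate for death, ED visits or transplant/VAD enters.

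**Step 3. Power for a broader event is unknown.** The documents give no control rate for a composite, so 40%, 50% and 60% at 180 days are assumptions. The method is that of Step 2 (comparison of proportions, one-sided 0.05).

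| Assumed control rate | Total N if the 30% reduction applies to every component | Total N if only readmission falls (10.5 points) | Power at 468, readmission-only case |
|---|---|---|---|
| 40% | 384 | 508 | 77% |
| 50% | 268 | 554 | 74% |
| 60% | 190 | 554 | 74% |

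The broader event could need fewer or more patients than 468. The documents do not settle which.

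**Step 4. Why time to readmission cannot replace Hypothesis 1b.** Assume constant hazards per 180 days: readmission a = 0.47 in both arms, death b = 0.10 in one arm and 0.20 in the other. Cumulative incidence of readmission is a/(a+b) × (1 − e^−(a+b)). The probability of readmission or death is 1 − e^−(a+b).

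- b = 0.10: readmission 0.47/0.57 × (1 − e^−0.57) = 35.8%; readmission or death 43.4%.
- b = 0.20: readmission 0.47/0.67 × (1 − e^−0.67) = 34.3%; readmission or death 48.8%.

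A cumulative-incidence comparison leans slightly towards the arm with more deaths. A cause-specific hazard comparison gives a ratio of 0.47/0.47 = 1 and does not register the deaths. The hazard ratio for readmission or death is 0.67/0.57 = 1.18 against that arm. Neither form of readmission analysis measures time to an event that includes death.

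**The case against.** The strongest reply is that Aim 1 never calls its list a composite and joins the components with a conjunction that could mean separate endpoints. On that reading the competing-risk analysis does address the rehospitalization part of Hypothesis 1b. This stands as far as it goes. But Study Purposes uses the disjunctive form for the time-to-event outcome, and Hypothesis 1b speaks of a first event. Even on the separate-endpoint reading, ED visits and time to death have no analysis.

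Four stronger readings are tempting, and the documents do not support them.

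- *A reader might infer that transplant/VAD was dropped from a defined composite or ruled out as a competing event.* Hypotheses 1a and 1b do not name it, and the Analyses section names no competing events, not even death. The accurate word is unspecified. A post-discharge transplant or implant would also ordinarily involve an admission (an inference), so few classifications are likely to change.
- *A reader might infer that the analyst could choose the endpoint after seeing the data.* The chi-square rule is explicit: death or at least one readmission by 6 months. It conflicts with the aims, but it is not left open.
- *A reader might infer that the plan hides deaths.* The chi-square test, listed first and ahead of those labelled secondary, counts them.
- *A reader might infer that the competing-risk analysis must favour the arm with more deaths.* That applies to cumulative incidence. The plan does not say which method it will use, and the illustrated shift is only 1.5 points (35.8% − 34.3%).

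**Conclusion.** The point holds in this form: ED visits have no planned analysis, Hypothesis 1b as a first-event outcome has no planned test, and the competing events in the readmission analysis are not named. This rests on the text and on no numerical assumption. Transplant/VAD is a lesser inconsistency, present in Aim 1 and the outcome list but absent from Hypotheses 1a and 1b and from the Analyses.

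The effect on the trial's result cannot be sized, because the documents give no rate for ED visits, death or any composite. The figures in Steps 3 and 4 are illustrations under stated assumptions. The main chi-square comparison is not invalidated. The plan should be changed on this point, but it does not undermine the trial as a whole.

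**What to change.** 1. Keep the chi-square test on death or readmission by 6 months as the main test.
2. Add, as the test of Hypothesis 1b, a Kaplan-Meier description with a log-rank or Cox comparison of time from discharge to the first of rehospitalization, ED visit or death, through 90 and 180 days. State whether transplant/VAD counts as an event, and word Aim 1 and Hypotheses 1a and 1b to agree.
3. Add a between-group comparison of the proportion with an ED visit at 45, 90 and 180 days.
4. Keep competing-risk time to readmission as supportive. Name the method, with death as a competing event, and transplant/VAD too if it is not counted as an event in item 2.
5. State in Sample Size that the trial is powered for rehospitalization only and that no power is claimed for the broader composite. This avoids having to supply control rates the documents do not contain.

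The cost is protocol wording plus one or two more secondary analyses on data already collected. The case report form is not in the documents, so check that it records the date of each ED visit.

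### The Poisson comparison of readmission rates makes no allowance for patients differing in readmission risk, so its standard errors are too small if the counts are overdispersed

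*Combined protocol and SAP*

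**What the plan says.** The Analyses section of the combined protocol and SAP is one paragraph. The comparison it names first is on a yes/no outcome, with the time point in months: "Pearson chi-square tests will be used to compare the proportion of subjects meeting the composite endpoint of death or at least 1 readmission by 6". Two secondary analyses follow. One is for counts: "Secondary analyses will use Poisson regression to compare readmission rates (number of readmissions/follow-up days"). The other is for first events: "competing risk survival methods will be used to compare time to first readmission between groups".

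Follow-up days enter the count model as exposure. Nothing else about that model is given: no scale parameter, robust variance, negative binomial alternative, patient-level effect or covariates, here or elsewhere in the document. The Charlson index (Outcomes and Measurement) is collected as medical history and to check that the groups are alike. It has no stated role in the model.

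On error rate, the section says "Analyses will be performed assuming a 0.05 significance level" and does not give sidedness. The Sample Size section does, for the power calculation only: "These calculations assumed a balanced randomization and use of one-sided Pearson chi-square tests with a significance level of 0.05".

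**The concern.** A Poisson model takes the variance of each patient's count, given follow-up, to equal its mean. If patients differ in underlying risk and the model does not capture it, the variance exceeds the mean and the model-based standard error of the rate ratio is too small. The follow-up-days exposure deals with unequal follow-up, not unequal risk.

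The plan describes a population in which risk can be expected to differ. Sample and Setting admits preserved and reduced ejection fraction, and NYHA class III and ambulatory IV, at three hospitals. Comorbidity is recorded in three levels. Feasibility says the two regional hospitals are less likely to have patients with advanced disease. The exclusions narrow this mix without removing it.

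If the counts are overdispersed, the interval for the readmission rate ratio is too narrow and the p-value too small. A chance imbalance in a few often-readmitted patients could then be reported as an effect of the card.

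**Working it through.** **Inputs from the plan (Sample Size section)**
- Control rehospitalization: "expected 90-day rehospitalization rate of 25% and a 180-day rehospitalization rate of 35"%.
- Effect: "minimum sample size needed to detect a decrease of 30% at 30-days, 90-days and 180-days", so 35% against 0.7 × 35% = 24.5% at 180 days.
- One-sided 5% chi-square test, 80% power, 1:1 allocation, 468 patients at 180 days before attrition.

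**Input not in the plan.** Overdispersion is an assumption. Each patient's rate is multiplied by a gamma variable with mean 1 and variance θ, with θ from 0 to 2.

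**Step 1: the plan's own 180-day figure.** Using the pooled-variance formula without continuity correction:

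n per group = [1.645√(2 × 0.2975 × 0.7025) + 0.8416√(0.35 × 0.65 + 0.245 × 0.755)]² / 0.105² = 233.3, rounded up to 234.

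The total is 468, which matches. The plan gives no power, standard error or dispersion for the Poisson comparison, so there is no figure for it to reproduce.

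**Step 2: anchor the counts to 35% readmitted by 180 days.** Setting P(0 readmissions) = 0.65 gives:
- Poisson: mean m = −ln 0.65 = 0.431.
- With heterogeneity: m = (0.65^−θ − 1)/θ.
- Variance/mean: V = 1 + θm.

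The Poisson standard error is too small by a factor √V. Therefore:
- two-sided error = 2[1 − Φ(1.96/√V)];
- one-sided error = 1 − Φ(1.645/√V);
- interval shortfall = 1 − 1/√V.

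Example, θ = 1: m = 1/0.65 − 1 = 0.538, V = 1.538 and √V = 1.240. The two-sided error is 2[1 − Φ(1.580)] = 0.114.

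| θ (assumed) | m | V | Two-sided 5% becomes | One-sided 5% becomes | Interval too narrow by | Readmitted 2+ times |
|---|---|---|---|---|---|---|
| 0 | 0.431 | 1.00 | 5.0% | 5.0% | 0% | 7.0% |
| 0.1 | 0.440 | 1.04 | 5.5% | 5.4% | 2% | 7.6% |
| 0.25 | 0.455 | 1.11 | 6.3% | 6.0% | 5% | 8.5% |
| 0.5 | 0.481 | 1.24 | 7.8% | 7.0% | 10% | 9.8% |
| 1 | 0.538 | 1.54 | 11.4% | 9.2% | 19% | 12.2% |
| 2 | 0.683 | 2.37 | 20.3% | 14.2% | 35% | 16.2% |

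The last column lets the sponsor judge which row is realistic from its own readmission data.

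**Step 3: simulation under no effect, two-sided 5%.** With 281, 441 and 533 per group, 20% uniform dropout and 10,000 to 20,000 replicates:

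| θ | Poisson error at 281 / 441 / 533 per group |
|---|---|
| 0 | 5.2% / 4.7% / 5.0% |
| 0.1 | 5.2% / 5.4% / 5.6% |
| 0.25 | 6.4% / 6.0% / 6.1% |
| 0.5 | 8.0% / 7.3% / 7.3% |
| 1 | 10.8% / 10.8% / 11.1% |
| 2 | 20.3% / 19.1% / 19.6% |

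Robust standard errors gave 4.6% to 5.5% throughout. A second simulation with full follow-up (234 and 484 per group, 8,000 runs) agreed with the formula, and robust standard errors gave 5.0% to 5.8%.

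**Step 4: cost when there is no heterogeneity.** With 281 per group, rate ratio 0.7, two-sided 5%, 20% dropout and 1,500 replicates (Monte Carlo standard error about 1.2 points), power is 68.5% for Poisson, 68.5% for robust Poisson and 67.8% for negative binomial. A repeat gave 66.9% for Poisson and 67.1% for robust Poisson.

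**What the planned rates can show.** The plan also says "a 30-day readmission rate of 18% is expected". At one constant rate, 18% by 30 days would imply 1 − 0.82⁶ = 69.6% by 180 days, against the 35% expected. Differing patient risk would produce this pattern, but so would a risk that falls over time for everyone, which alone does not overdisperse counts. It is not proof.

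**The case against.** - **The size has no source in the documents.** This stands. They give no count data and no repeat-readmission share, and at θ of 0.1 to 0.25 the two-sided error is only 5.5% to 6.3%. The answer is to choose a method that is valid either way.
- **The evidence of heterogeneity is indirect.** This partly stands. The Charlson index is tied to mortality, three hospitals do not by themselves show different readmission risk, and the exclusions remove several high-risk groups. Overdispersion is plausible, not derived from the documents.
- **The two-sided figures are the larger ones.** The only sidedness in the plan is one-sided, for sample size. On that basis the worst case shown is about 14%, not 20%. Both are given above because Analyses does not settle the matter.
- **Little depends on this analysis.** This stands. Hypotheses 1a and 1b concern first occurrence and time to first event, and no stated hypothesis concerns a count or rate. It is, however, the only planned analysis that uses repeat readmissions.
- **Naming Poisson regression does not exclude a scaled or robust variance.** True, but the plan does not state one. Leaving the choice until the data are seen is what pre-specification should prevent.

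**Conclusion.** The concern holds in its conditional form. As written, the readmission-rate comparison has standard errors that are too small to whatever extent the counts are overdispersed. The understatement is a factor of 1.02 to 1.54 over the assumed range (√V for θ from 0.1 to 2), and none if patients do not differ in risk. This rests on gamma heterogeneity, on the plan's 35% at 180 days and, for the formula figures, on full follow-up.

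The chi-square composite and the time-to-first-readmission analysis use one outcome per patient and are unaffected, as is the sample size. This is an optional, low-cost improvement to a secondary analysis.

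**What to change.** In Analyses, replace the Poisson clause with one named method, for example: Readmission counts will be compared between groups by Poisson regression with robust (sandwich) standard errors and log follow-up days as offset.

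Negative binomial regression would also serve: at θ = 1 and 281 per group, both it and robust Poisson gave a simulated two-sided error of 4.8%, against 10.0% for ordinary Poisson. The plan should name one of them, so that both are not run and one picked afterwards. It should also say whether the test is one- or two-sided.

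The cost is one sentence, with no new data, patients or procedures. If counts are overdispersed, the interval widens to its correct width. If they are not, the simulations show no detectable loss of power with robust Poisson.

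### About 18 to 37 correlated comparisons share one unadjusted 0.05 level, and the implied lead test is never designated primary and matches neither the hypotheses nor the sample-size endpoint

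*Combined protocol and SAP*

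**What the plan says.** The Analyses section has one sentence on error control: "Analyses will be performed assuming a 0.05 significance level". It does not say whether this is one- or two-sided, and neither it nor any other section gives an adjustment, hierarchy or gatekeeping rule.

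That section opens its group comparisons with a Pearson chi-square test on a composite of death or one or more readmissions by 6 months. It then labels as secondary a Poisson model of readmission rates and a competing-risk analysis of time to first readmission. The word primary is attached to none of the trial's endpoints.

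The Study Purposes and the Specific aims and hypotheses are much broader. The purposes include time to "first occurrence of all-cause and HF hospitalization, ED visit, or death/cardiac transplantation or VAD implant" at 45, 90 and 180 days, as well as occurrence at the same windows. Hypothesis 1a says that 45-day events "will be lower or trend toward lower", and that 90- and 180-day occurrence will be lower. Hypothesis 1b covers time to first event at 90 and 180 days. Hypothesis 2a names seven KCCQ scores: "clinical summary score, quality of life score, total symptom score -and subscales of physical limitations, symptom stability, symptom frequency, and symptom burden". Hypotheses 2b to 2d add symptom count, functional status and activity level, and Hypothesis 3 adds the 7-day appointment.

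The Sample Size section uses rehospitalization alone, at three time points: "A total sample size of 968, 734 and 468 are needed to achieve 80% power in 30-day, 90-day and 180-day rehospitalization rates, respectively". It assumes "use of one-sided Pearson chi-square tests with a significance level of 0.05".

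**The concern.** The hypotheses, the sample size and the analysis point to different endpoints, and nothing ranks them:

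- **Hypotheses:** separately named clinical events, with death grouped with transplantation or VAD. The death-or-readmission composite is not listed.
- **Sample size:** rehospitalization alone, with significant differences expected at both 90 and 180 days.
- **Analysis:** death or readmission by 6 months.

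An investigator who follows the plan as written could therefore present any one favourable result as the trial's success. Hypothesis 2a has the same gap on a smaller scale, because it does not say whether one score or all seven must differ. The wording about a trend in Hypothesis 1a also lets a non-significant 45-day difference be reported as support.

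At stake is the meaning of a significant result from this trial. Its error rate depends on which comparison is brought forward after the data are seen, and a reader could not recover that rate from the plan.

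**Working it through.** **The plan's own figures.** The documents state no family-wise error rate. The only related figures that can be reproduced are the sample sizes. With a one-sided 0.05 pooled chi-square test without continuity correction, 80% power, 1:1 allocation and a 30% relative reduction:

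- 25% vs 17.5% gives 734 in total, as stated.
- 35% vs 24.5% gives 468, as stated.
- 18% vs 12.6% gives 1098, not 968. The stated 968 is the result for 20% vs 14%.

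The last discrepancy is a separate matter and does not enter what follows. What matters here is that all three calculations are for rehospitalization and none is for the composite.

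**Counting comparisons.** The count is inferred from the aims and hypotheses, since the Analyses section itself specifies only three analyses.

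| Source | Events combined | Events separate |
|---|---|---|
| First occurrence | 1 × 3 windows = 3 | 4 outcomes × 3 windows = 12 |
| Time to first event | 1 × 2 windows = 2 | 4 × 2 or 3 windows = 8 to 12 |
| KCCQ scores (2a) | 7 | 7 |
| Symptoms, function, activity (2b-2d) | 3 | 3 |
| 7-day appointment (3) | 1 | 1 |
| Composite and Poisson | 2 | 2 |
| **Total** | **18** | **33 to 37** |

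The four separate outcomes are all-cause hospitalization, HF hospitalization, ED visit, and death/transplant/VAD.

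**Expected false positives under no effect.** This equals m × 0.05 whatever the correlation: 18 × 0.05 = 0.90, 33 × 0.05 = 1.65, 37 × 0.05 = 1.85.

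**Chance of at least one, if independent.** This is 1 − 0.95^m: 60% for 18, 82% for 33, 85% for 37.

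**Chance of at least one, with correlation.** The tests overlap heavily: the windows are nested, occurrence and time to event use the same events, HF admissions are part of all-cause admissions, and the KCCQ scores share items. The documents give no correlations, so a range is assumed. Simulated equicorrelated normal test statistics, each tested at two-sided 0.05, give:

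| Assumed correlation | 18 tests | 33 tests | 37 tests |
|---|---|---|---|
| 0.3 | 51% | 69% | 72% |
| 0.5 | 40% | 53% | 56% |
| 0.7 | 28% | 35% | 37% |

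A block structure that separates clinical events from patient-reported measures (also assumed) gives 39-65% two-sided for 33-37 tests and 33-56% if all tests are one-sided at 0.05. Counting only false positives that favour the card, at two-sided 0.05, gives about 20-37%.

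**Seven KCCQ scores alone.** If any one score suffices, 1 − 0.95^7 = 30% if independent. The simulated figure is 23% at correlation 0.5, 18% at 0.7 and 15% at 0.8. If all seven must differ, the error rate cannot exceed 5%.

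**Bonferroni over everything is not a sensible remedy.** The per-test level would be 0.05/33 = 0.0015 or 0.05/37 = 0.00135. With 468 patients, the 180-day rehospitalization comparison would then have about 23-24% power two-sided, against 80% at one-sided 0.05.

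**The case against.** The strongest reply is that a lead test can be identified. The Analyses section begins with one composite at 6 months and calls the next analyses secondary. A reader might infer that the plan has no confirmatory test at all; that section does not support so strong a statement. What stands is narrower: the lead test is never called primary, does not appear among the hypotheses and is not the endpoint that was sized.

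Second, a reader might infer that a chance significant finding is more likely than not. That follows only under independence or the lower assumed correlations. With the overlap among these outcomes the figure may lie on either side of 50%, and it is lower still if only results favouring the card are counted.

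Third, 33-37 is one reading. Hypothesis 1b can fairly be read as a single combined event, and Hypotheses 1a and 1b do not separate all-cause from HF events. The lower count of 18 is therefore legitimate, and the plan does not settle which applies.

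Fourth, the trend wording has an explanation. The Sample Size section expects only a trend early on and significance at 90 days and 6 months, so the phrase mostly forgoes an early claim. It adds nothing to the calculated error rates. It remains loose, because it sits inside a hypothesis and could be used to report support.

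Finally, restricting significance claims elsewhere is partly a choice. The 90-day comparison is hypothesized and has its own sample size, so the fix should leave a route for it.

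**Conclusion.** The concern holds in this form: many correlated comparisons fall under one unadjusted 0.05 level, and the implied lead test is neither designated primary nor aligned with the hypotheses or the sample size. The family-wise error rate is well above 5% under every count and correlation examined: 60-85% if independent, and roughly 28-72% two-sided at correlations of 0.3-0.7. For Hypothesis 2a alone it is 15-23% at correlations of 0.5-0.8 on the any-one-score reading, and not inflated on the all-seven reading.

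These sizes rest on assumed correlations, on a count inferred from the hypotheses, and on applying the general 0.05 sentence to outcomes for which the plan names no test. The lack of a designated primary test depends on none of these assumptions. This should be corrected, but it does not invalidate the design.

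**What to change.** 1. In Analyses, designate the 6-month composite of death or readmission as the single primary test, state whether its 0.05 is one- or two-sided, and reword Hypothesis 1 to match.
2. Make the KCCQ clinical summary score the only Hypothesis 2a endpoint; the Outcomes and Measurement section already cites a 5-point benchmark for it. Treat the other six scores as supportive.
3. Apply Holm across the four Aim 2 measures (KCCQ clinical summary, symptoms, DASI, activity). The ordered p-values are compared with 0.05/4 = 0.0125, 0.05/3 = 0.0167, 0.05/2 = 0.025 and 0.05.
4. Label the other windows, the component events and the 7-day appointment as secondary, and report them as estimates with confidence intervals. If a confirmatory 90-day claim is wanted, test it only after the 180-day primary test succeeds.
5. State that a non-significant 45-day trend does not count as support.

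This needs no new data or procedures. The cost is that fewer results can be called significant. The primary test and the Aim 2 family each carry 0.05, so across both the error is bounded by 0.10; the plan should say that this is accepted, or test Aim 2 only after the primary succeeds. The Sample Size section should also note that its power figures apply to rehospitalization, not to the composite.
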